This study is a randomized, controlled trial with a parallel group design, focusing on the utilization of SIGHT in a pediatric clinical setting. The trial employs a superiority framework to evaluate the effectiveness of SIGHT in enhancing clinical decision-making regarding genetic testing. Randomization will be assigned in a 1:1 allocation ratio to either the intervention group, receiving a SIGHT-prompted provider message, or the control group, receiving usual care without the SIGHT-prompted message. The randomization process will be automated with SIGHT scores generated prior to regular scheduled patient visits at the POD-C pediatric primary care clinic at the Vanderbilt University Medical Center (VUMC) One Hundred Oaks location (OHO).

This trial design allows for a robust comparison between the standard approach to genetic testing and an innovative, data-driven strategy facilitated by SIGHT. The primary objective is to assess whether the SIGHT model can effectively increase the number of patients who receive a genetic diagnosis, while potentially decreasing the time to genetic testing and increasing diagnostic yield in pediatric patients.

Methods: Participants, interventions, and outcomes

9

Study setting

Description of study settings (eg, community clinic, academic hospital) and list of countries where data will be collected. Reference to where list of study sites can be obtained

The study will take place in Nashville TN and consist of pediatric patients visiting the POD-C pediatric primary care clinic at the Vanderbilt University Medical Center (VUMC) One Hundred Oaks location (OHO as part of the usual course of care.

Eligibility criteria

10

11a

Inclusion and exclusion criteria for participants. If applicable, eligibility criteria for study centres and individuals who will perform the interventions (eg, surgeons, psychotherapists)

Inclusion criteria will consist of patients > 1 year old, < 20 years of age with a visit to the POD-C pediatric primary care clinic at the Vanderbilt University Medical Center (VUMC) One Hundred Oaks location (OHO.

Exclusion criteria will consist of patients who have been programmatically excluded due to having already received a chromosomal microarray at VUMC, and patients > 20 years of age and < 1 year of age

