11c Strategies to improve adherence to intervention protocols, and any procedures for monitoring adherence (eg, drug tablet return, laboratory tests)

Adherence meetings are held prior to study implementation with POD-C physicians. These providers will be more likely to provide constant care in the clinic over the duration of the study as opposed to those physicians who have interim appointments. The Directors of the POD-C clinic can also request an education session at any time or new provider training if needed. Additionally, training materials will be readily accessible via all SIGHT provider prompted messaging. Strategies to improve adherence for the pediatric patients flagged by the SIGHT model is not applicable as they will follow usual care at VUMC and will not be consented and enrolled by the study team.

11d Relevant concomitant care and interventions that are permitted or prohibited during the trial

Usual pediatric care and treatments that are unrelated to genetic testing are permitted and expected to continue as normal. Interventions and treatments necessary for the immediate health and well-being of the patient, regardless of their relation to genetic testing, are anticipated as part of usual care. Any intervention by the study team that could influence the healthcare provider's decision-making process regarding genetic testing, outside of the SIGHT model's recommendations will be avoided. Interventions specifically aimed at influencing the study outcomes, such as additional prompts or incentives for genetic testing are prohibited.

Outcomes

12

Primary, secondary, and other outcomes, including the specific measurement variable (eg, systolic blood pressure), analysis metric (eg, change from baseline, final value, time to event), method of aggregation (eg, median, proportion), and time point for each outcome. Explanation of the clinical relevance of chosen efficacy and harm outcomes is strongly recommended

Primary Outcome:

Specific Measurement Variable: Number of patients

diagnosed via a Chromosomal Microarray.

Analysis Metric: Chi-square test.

Method of Aggregation: Direct case control comparison of the raw count of patients diagnosed, presented as a percentage. **Time Point:** Assessed after one year to include enough time for patients to undergo testing through usual care.

Secondary Outcomes:

Specific Measurement Variable: Duration of time to genetic testing.

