 - **5. Study Close-Out:** Final Assessment: Conducted at the end of the study period to collect the final data on all outcomes.

Sample size

14 Estimated number of participants needed to achieve study objectives and how it was determined, including clinical and statistical assumptions supporting any sample size calculations

Previous data suggest that, under the usual course of care, 9% of high-risk patients (those with a predicted score of ≥ 0.3) had genetic testing. Of those, 9% received a genetic diagnosis, resulting in a genetic diagnosis rate of 0.81% (0.09*0.09) among high-risk patients

One thousand high-risk patients (score \geq 0.3) will be randomized 1:1 (500 per arm). This sample size provides 80% power to detect an increase in the genetic diagnosis rate from 0.81% under standard care to at least 3.6% with the SIGHT intervention (chi-square test, α =0.05)

Recruitment 15 Strategies for achieving adequate participant enrolment to reach target sample size

The VUMC POD-C pediatric clinic has had over 200,000 patient encounters from over the last five years with more than 30,000 unique patients and over 10,000 unique patients in 2023. The clinic averages 144 visits per day (median = 165). Estimates indicate potentially 1-2 patients flagged per day which should readily provide enough patients for an adequate sample size over a two to three-year period.

Methods: Assignment of interventions (for controlled trials)

Allocation: Sequence generation 16a

Method of generating the allocation sequence (eg, computer-generated random numbers), and list of any factors for stratification. To reduce predictability of a random sequence, details of any planned restriction (eg, blocking) should be provided in a separate document that is unavailable to those who enrol participants or assign interventions.

The SIGHT study will utilize a computer-generated assignment schedule for all patients seen in the POD-C pediatric clinic with a score greater than or equal to 0.3 for allocation into the intervention group. A computer-generated randomization schedule will be used for assigning participants to the control group. This is completed using the built-in random module of python, assigning patients with equal scores either 0 (control) or 1 (intervention) to each patient who has met all previously defined criteria, with assignments saved to a log file.

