The allocation sequence will be generated by the study's data management team using a computer-based randomization function. Any pediatric patient scheduled for a visit in the POD-C pediatric primary care clinic at VUMC One Hundred Oaks (OHO) who meets or exceeds the predefined risk threshold will be flagged as eligible. These flagged patients will then be randomly assigned to either the intervention arm (SIGHT-prompted provider message) or the usual care arm (no provider message).

Participant Enrollment

Patients aged 1 to 20 years who have not previously undergone chromosomal microarray testing at VUMC will be automatically included in the randomization pool once they have a scheduled visit at the OHO clinic. As this study follows standard clinical care, patients themselves do not undergo a separate consent process for randomization. Instead, their providers will be informed of any SIGHT alerts only if the patient is randomized to receive them.

Assignment of Participants to Interventions

For those randomized to the intervention arm, a SIGHT-prompted provider message is generated within EPIC by a genetic counselor on the research team. This message indicates the patient's increased risk level and recommends considering a chromosomal microarray and referral to genetics. The provider maintains full discretion to act upon or dismiss this recommendation. By contrast, providers in the usual care arm receive no automated messages about SIGHT risk, and patients continue under routine care practices.

Concealment of Allocation

The randomization process is integrated into the workflow so that neither providers nor the study team can predict a patient's assignment prior to the system's automated allocation. This design ensures there is no foreknowledge of group assignment—preventing selection bias and preserving the trial's integrity.

Blinding (masking)

17a

Who will be blinded after assignment to interventions (eg, trial participants, care providers, outcome assessors, data analysts), and how

There will be no blinding of participants or physicians as patients and providers will follow usual care. Providers may dismiss the SIGHT – prompted provider message and not act on its recommendations at any time. No other intervention is planned. Patients would be unaware of the providers' decisions in that case unless the provider chooses independently to discuss the SIGHT score with them.

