There will be no plan to promote participant retention and complete follow-up as patients are following usual care and may or may not undergo genetic testing as per the choice of the patient and family.

Data management

19

Plans for data entry, coding, security, and storage, including any related processes to promote data quality (eg, double data entry; range checks for data values). Reference to where details of data management procedures can be found, if not in the protocol

Data will be extracted EPIC's Clarity and then stored on VUMC's ACCRE cluster, which is designed for secure handling of export-controlled data, PHI, and human genotype and phenotype data. EPIC's Clarity and the ACCRE cluster feature rigorous backup protocols ensuring data integrity and recovery. Details of data management procedures, including security protocols, access controls, and data backup schedules, are detailed at https://www.vanderbilt.edu/accre/overview/.

Statistical methods

20a

Statistical methods for analysing primary and secondary outcomes. Reference to where other details of the statistical analysis plan can be found, if not in the protocol

The primary and secondary outcomes of this trial will be analyzed using appropriate statistical tests to compare the intervention arm (SIGHT-prompted provider message) against the control (patients receiving usual care provided through the POD-C pediatric primary care clinic at the Vanderbilt University Medical Center (VUMC) One Hundred Oaks location (OHO). The primary outcome measure will be the difference in number of patients who receive diagnoses via a Chromosomal Microarray between the two groups.

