c. Diagnosis via any test (molecular confirmation)	More patients will receive a diagnosis from molecular confirmation outside of firs tier testing via a CMA.	Number of patients flagged by SIGHT who receive a diagnosis via any test over one year vs controls [binary]	Chi-square test
d. Adherence to Intervention	Providers who Receive SIGHT prompts demonstrate higher adherence recommendations compared to controls	Proportion of eligible patients where providers ordered a CMA and place genetics referrals after receiving a prompt [binary]	Chi-square test; logistic regression adjusting for covariates

20b Methods for any additional analyses (eg, subgroup and adjusted analyses)

Subgroup analysis within demographic groups (sex, race, age) will be performed as described in the primary analysis but within each group or stratified by age.

Definition of analysis population relating to protocol nonadherence (eg, as randomised analysis), and any statistical methods to handle missing data (eg, multiple imputation)

Non-adherence and missing data for the SIGHT protocol are non-applicable in this context as patients will follow usual care. Patients who are lost to follow up or have no follow up care during the duration of the study will remain included in the analysis.

Methods: Monitoring

Data monitoring 21a

Composition of data monitoring committee (DMC); summary of its role and reporting structure; statement of whether it is independent from the sponsor and competing interests; and reference to where further details about its charter can be found, if not in the protocol. Alternatively, an explanation of why a DMC is not needed.

This study does not require a DMC as the protocol presents minimal risks to participants and adverse events or other problems are not anticipated. In the unlikely event that such events occur, unanticipated problems involving risks to subjects or others will be reported immediately to the PI and and within 7 days of the PI's notification of the event to the IRB.

21b Description of any interim analyses and stopping guidelines, including who will have access to these interim results and make the final decision to terminate the trial

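### The primary objective is more genetic diagnoses, but the primary outcome counts only microarray diagnoses, so the primary result does not by itself answer the objective

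*Protocol*

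**What the plan says.** - **Objective.** Item 8 (Trial design): "The primary objective is to assess whether the SIGHT model can effectively increase the number of patients who receive a genetic diagnosis". It does not restrict the diagnosis to one test.
- **Primary outcome.** Item 12 counts patients "diagnosed via a Chromosomal Microarray". Item 20a agrees: "The primary outcome measure will be the difference in number of patients who receive diagnoses via a Chromosomal Microarray between the two groups". The item 20a table and the registration table at the end also name CMA.
- **Any-test diagnosis.** This is a secondary outcome in item 12, in row c of the item 20a table and in the registration table.
- **Intervention.** Under item 16c the message "recommends considering a chromosomal microarray and referral to genetics". Usual-care providers receive no message.
- **Sample size.** Item 14 starts from "9% of high-risk patients (those with a predicted score of ≥ 0.3) had genetic testing". It then takes a 9% yield among those tested, "resulting in a genetic diagnosis rate of 0.81% (0.09*0.09) among high-risk patients", and powers a rise to 3.6% with 500 per arm. It does not say whether the two 9% figures refer to CMA or to all genetic tests.

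**The concern.** The protocol itself treats CMA diagnosis and any-test diagnosis as different quantities. The stated objective fits the second, and the primary test addresses the first. The gap matters because the intervention acts on it: one arm is pointed to the test that counts and the other is not.

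The error can run in two directions:

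- **Overstatement.** A usual-care child diagnosed by another test counts as undiagnosed. If the message leads such children to be diagnosed by CMA instead, CMA diagnoses rise with no additional child diagnosed.
- **Understatement.** The message also recommends referral. If the genetics clinic reaches a diagnosis by another test, the primary outcome misses it.

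At stake is what may be concluded. A significant primary result would not establish the item 8 objective, and a null one would not refute it. Nothing in the protocol makes the primary conclusion depend on the any-test comparison.

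**Working it through.** **1. The plan's own figure.** Inputs from item 14: p1 = 0.09 × 0.09 = 0.0081, p2 = 0.036, 500 per arm, alpha 0.05; two-sided from item 20a.

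n = [1.96·√(2p̄(1−p̄)) + 0.84·√(p1(1−p1) + p2(1−p2))]² / (p2−p1)², with p̄ = 0.02205, gives 434 per arm. The continuity-corrected version, (n/4)·[1 + √(1 + 4/(n(p2−p1)))]², gives 503, close to the planned 500. Uncorrected power at 500 is 85.3%. The arithmetic is sound; the question is which endpoint the rates describe.

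**2. Substitution with no extra diagnosis.** Assumptions, none of them in the protocol: the any-test diagnosis rate T is the same in both arms, every message-arm diagnosis comes by CMA, and a share s of control diagnoses comes by CMA. The CMA rates are then s·T (control) and T (message). The table sums the exact binomial probabilities, at 500 per arm, of all outcomes where the chi-square exceeds 3.84 in favour of SIGHT.

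| T in both arms | s | Expected CMA diagnoses, control vs message | Uncorrected | Continuity-corrected |
|---|---|---|---|---|
| 0.81% | 1 (no switch) | 4.05 vs 4.05 | 2.2% | 0.9% |
| 0.81% | 1/2 | 2.0 vs 4.05 | 11% | 5% |
| 0.81% | 1/3 | 1.35 vs 4.05 | 20% | 8% |
| 2% | 1/2 | 5 vs 10 | 24% | 16% |
| 2% | 1/3 | 3.3 vs 10 | 44% | 34% |
| 3% | 1/2 | 7.5 vs 15 | 36% | 27% |
| 3% | 1/3 | 5 vs 15 | 64% | 53% |

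The 0.81% rows use the protocol's usual-care rate. The 2% and 3% rows are about 2.5 and 3.7 times that rate.

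**3. The other direction.** Suppose the any-test rate really rises from 0.81% to 3.6%, all control diagnoses are by CMA, and half of message-arm diagnoses come by another test after referral. The CMA comparison is then 0.81% against 1.8%, and its power is 26% (18% corrected), although the planned gain is real.

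**4. If the item 14 rates cover all tests.** Suppose half of diagnoses in both arms are by CMA. The CMA rates become 0.405% and 1.8%, with p̄ = 0.011025.

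Power = Φ[(0.01395·√500 − 1.96·√(2p̄(1−p̄))) / √(p1(1−p1) + p2(1−p2))] = Φ[(0.3119 − 0.2894)/0.1473] = Φ(0.153) = 56%, against 85.3% in step 1 (both uncorrected). The number for 80% power, uncorrected, would be 879 per arm.

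**The case against.** The CMA primary is used consistently in items 12 and 20a and the registration table. It suits the design: prior CMA is the exclusion, and the item 7 objective is about CMA testing. That stands, and it is a reason to keep the outcome and correct the objective.

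A reader might infer that 0.81% cannot be a CMA rate. The document does not support that. Item 14 speaks of genetic testing without saying all tests, and items 7 and 18a both describe the testing of interest as CMA. The figures may be CMA figures; item 14 does not say.

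A reader might also infer that switching is likely to produce a false success. The document does not show this either. It gives no usual-care test mix and does not say that a child diagnosed by another test would also be diagnosed by CMA. Item 7 describes the message more broadly, as recommending a genetic test, and item 11a leaves providers full discretion. Row c calls CMA first-tier, which sits poorly with a control share as low as one third. At 0.81% only about 4 expected diagnoses per arm could switch, whereas the planned difference is (3.6% − 0.81%) × 500, or about 14. Switching alone could not produce the planned effect.

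Finally, the any-test secondary outcome would help to expose a pure switch. That is true, but it does not govern the primary conclusion.

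**Conclusion.** The point holds as a mismatch between objective and primary outcome that bears on the claim the trial may make. It does not depend on how item 14 is read. Its numerical size cannot be fixed from the protocol. At the planning rate, with complete substitution and a control CMA share of one third to one half, the chance of a significant result without any extra diagnosis is 11% to 20% uncorrected, or 5% to 8% corrected. The larger figures in the table need a total diagnosis rate well above the protocol's. Complete substitution is an upper-end assumption throughout, and the referral route can bias the result the other way.

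One might conclude that any-test diagnosis should replace the primary outcome. That does not follow. The trial is recruiting with CMA as its registered primary, and the any-test outcome is not yet defined consistently: the row c hypothesis concerns diagnoses outside CMA, its measure covers any test, and item 12 and the registration table add clinical diagnosis.

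**What to change.** Keep the registered CMA primary outcome and make four changes to the text:

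1. In item 8, reword the primary objective to *diagnosis by chromosomal microarray*.
2. In item 20a, state that an increase in genetic diagnoses overall will be claimed only if the any-test comparison also favours SIGHT.
3. Define that comparison once, with CMA included. Reconcile the row c hypothesis, the row c measure, and the clinical-diagnosis wording in item 12 and the registration table.
4. In item 14, state whether the two 9% figures are for CMA or for all genetic tests. If they are not CMA figures, give the CMA rates and restate the power.

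The cost is wording in an amendment, with no new patients and no new data, since any-test diagnosis is already a planned outcome and item 18a already provides for chart review of test results. The downside is a narrower claim and possibly a less favourable stated power.

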Analysis Metric: Time to event, measured from the initial patient visit to the time genetic testing is conducted.

Method of Aggregation: Median time in days

Specific Measurement Variable: Rates of genetic testing. **Analysis Metric:** Proportion of patients who received testing **Method of Aggregation:** Proportion of patients, presented as a percentage

Time Point: Assessed after one year to include enough time for patients to undergo testing through the usual course of care.

Specific Measurement Variable: Diagnosis via any genetic testing.

Analysis Metric: Proportion of patients diagnosed with a genetic disease following molecular testing or clinical evaluation. **Method of Aggregation:** Proportion of patients, presented as a percentage.

Time Point: Assessed after one year to include enough time for patients to undergo additional testing through usual care.

Specific Measurement Variable: Adherence to the SIGHT-prompted provider message.

Analysis Metric: Frequency of provider actions via referral to genetics and ordering a patient CMA following receipt of a SIGHT-prompted message.

Method of Aggregation: Proportion of instances where the provider follows the SIGHT recommendation.

Time Point: Information will be collected at the end of the study.

Participant timeline

- Time schedule of enrolment, interventions (including any run-ins and washouts), assessments, and visits for participants. A schematic diagram is highly recommended (see Figure)
 - 1. Enrollment Process: Eligibility Screening: Conducted at the initial patient visit. Consent Process: Following eligibility screening, informed consent will not be obtained as patients are following usual care.
 - **2. Interventions:** SIGHT-Prompted Provider Message: Initiated following screening for patients who meet the predefined risk threshold.
 - 3. Assessments: Baseline Assessment: Conducted during the initial visit, including collection of patient health data. Follow-up Assessments: Scheduled after initial visit to monitor the outcomes, such as number of patients receiving a diagnosis, time to genetic testing, and diagnostic yield.
 - 4. Visits: Initial Visit: SIGHT prompted provider message followed by review of referrals and documentation attributable to the initial patient visit. Subsequent Visits: Regular follow-ups as per usual pediatric care, during which recommendations and any genetic testing decisions are documented and assessed.

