The statistical analysis will utilize a chi-square test for binary outcomes such as the presence or absence of a genetic diagnosis as identified by the test or provider adherence to SIGHT message recommendations. For continuous secondary outcomes, such as the time to genetic testing, a T-test or Mann-Whitney U test will be used depending on data distribution. Subgroup analyses will involve regression methods to assess the differential effects of the intervention across subgroups defined by baseline demographic characteristics (e.g. age, sex, race). Multivariate analyses will be conducted using logistic regression for binary outcomes and linear or Cox proportional hazards regression for continuous or time-to-event outcomes, respectively. Model assumptions will be checked through the assessment of residuals and model fit will be evaluated accordingly.

When indicated, a two-sided p-value of less than 0.05 will be considered statistically significant. The Bonferroni correction will be applied to account for multiple comparisons when analyzing multiple outcomes. R will be used to perform all analyses. The analysis plan will follow the intention-to-treat principle, with all randomized participants included in the analysis according to the group to which they were allocated.

Variable/outcome	Hypothesis	Outcome measure	Methods of analysis
Primary			R will be used to perform all analysis.
Number of diagnoses via CMA	More patients are diagnosed being flagged by SIGHT via a Chromosomal Microarray	Number of patients flagged by SIGHT who receive a diagnosis via CMA over one year vs controls [binary]	Chi-square test
Secondary			
a. Time to genetic test	Patients in the intervention arm will receive genetic testing faster than those in the controlarm.	Duration in days for which patients flagged by SIGHT receive a genetic test vs control [continuous]	Cox proportional Hazards to compare the time to event (in this case genetic testing) between two groups while controlling for covariates.
b. Rates of genetic testing	Increased rates of genetic testing in the intervention arm	Rates of genetic testing ordered by providers between cases and controls over a one-year period after POD-C visit [continuous'	Binary logistic regression to calculate the odds ratio for the likelihood of receiving a genetic test in the intervention arm compared to the controls

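### The median in days fixed for time to genetic testing will not be reached in the usual-care arm, so it cannot compare the arms unless it is confined to tested patients

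*Protocol*

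**What the plan says.** Item 12 of the Protocol (Outcomes, first secondary outcome) defines the variable as "Time to event, measured from the initial patient visit to the time genetic testing is conducted" and gives its summary as "Method of Aggregation: Median time in days". Unlike the testing-rate and diagnosis outcomes listed after it, this one has no time point of its own. The Protocol does not say how patients who are never tested enter the median.

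Item 14 (Sample size) reports from earlier data that "9% of high-risk patients (those with a predicted score of ≥ 0.3) had genetic testing". It continues: "Of those, 9% received a genetic diagnosis, resulting in a genetic diagnosis rate of 0.81% (0.09*0.09) among high-risk patients". The trial is sized at 500 per arm to detect a rise to at least 3.6%.

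Item 20a treats the outcome in two ways. The text classes it as continuous and names a t-test or Mann-Whitney test. Row a of the table also labels it continuous but names a Cox model, under the hypothesis "Patients in the intervention arm will receive genetic testing faster than those in the controlarm". The same item states that all randomised participants are analysed in their allocated group.

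**The concern.** Shortening the time to testing is one of the aims in item 7. A median time to event exists only once half of the group has had the event, and the Protocol's own rates put the usual-care arm far below half. Two outcomes follow. If the median is taken over all randomised patients, at least one arm has no value and the medians cannot be compared. If it is taken only among tested patients, a number appears for each arm, but the message is designed to change who gets tested, so the two tested groups are no longer comparable by randomisation. The continuous label and the t-test or Mann-Whitney sentence in item 20a make that second reading easy to fall into.

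**Working it through.** **Inputs.** From item 14: 9% tested under usual care, 9% of those diagnosed, target diagnosis rate 3.6%, 500 per arm, 80% power, α = 0.05. From item 20a: two-sided test, all randomised patients analysed. The one-year horizon is borrowed from the neighbouring outcomes in item 12. Item 14 does not state the period behind the 9%.

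**1. The plan's own figures.** Base rate: 0.09 × 0.09 = 0.81%. For 0.81% against 3.6%, the usual two-proportion formula gives

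n = [1.960 × √(2 × 0.02205 × 0.97795) + 0.842 × √(0.0081 × 0.9919 + 0.036 × 0.964)]² / 0.0279² = 434 per arm,

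or 503 with continuity correction. The stated 500 is consistent with the corrected figure, and the sample size is not in question.

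**2. Share tested in each arm.**
- Control: 9%, or 0.09 × 500 = 45 patients.
- Message: diagnosis rate / yield = 0.036 / 0.09 = 40%, or 200 patients. This is derived by holding yield at 9%. The Protocol states no such rate.

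Both are below 50%. If the true share is 40%, the binomial chance that at least 250 of 500 are tested is about 4 in a million. At 9% it is effectively zero.

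**3. Sensitivity to yield, message arm at a 3.6% diagnosis rate.**

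| Yield among tested | Share tested |
|---|---|
| 6% | 60% |
| 7.2% | 50% |
| 8% | 45% |
| 9% | 40% |
| 12% | 30% |

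The message arm reaches a median only at a yield of 7.2% or less. The Protocol hopes to raise yield, which lowers the share tested. The control arm's 9% does not depend on this.

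**4. Sensitivity to the time scale.** Assume constant hazards and that 9% is a one-year rate. The medians are then ln 2 / −ln(0.91) = 7.3 years in controls and ln 2 / −ln(0.60) = 1.36 years with the message. For the control median to fall within a year, the 9% would have to accrue in ln(0.91)/ln(0.50) × 365 ≈ 50 days or less.

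**5. What a tested-only median would show.**

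*Constant hazards.* Among those tested within the year, the medians are −ln(1 − 0.045)/0.0943 × 365 = 178 days (control) and −ln(1 − 0.20)/0.5108 × 365 = 159 days (message). The hazard ratio is 0.5108/0.0943 = 5.4, so most of the effect disappears from view.

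*Two kinds of tested patient (timings assumed; none are in the Protocol).* The 9% who would be tested anyway have exponential times with median 60 days, truncated at day 365. With the message each of them is tested 30% sooner. A further 31% are tested only because of the message. The control median among the tested is 59 days.

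| Assumed median of message-induced tests | Message-arm median among tested |
|---|---|
| 40 days | 40 days |
| 60 days | 54 days |
| 180 days | 96 days |

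The direction reverses once the assumed median exceeds about 68 days, although nobody is tested later with the message than without it.

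*Summaries over all randomised patients, 180-day case.* Cumulative percentage tested is 2.7% against 8.0% by day 30 and 5.9% against 19.1% by day 90. Mean untested days up to day 365 are 339 against 268. These exist in both arms and favour the message.

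**The case against.** The strongest reply is that the analysis does not hang on the median. Row a plans a Cox comparison, which uses all randomised patients with the untested censored, and item 12 separately lists the proportion tested at one year. If the median is not reached, the trial still reports both. This stands, and it confines the point to the fixed summary of a secondary outcome. It does not rescue that summary.

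Three stronger readings are tempting, and the document does not support them.

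- *The median exists in neither arm.* This is established for controls only. The 40% in the message arm is derived, 3.6% is worded as a minimum, item 12 sets no time point for this outcome, and recruitment runs two to three years. Larger effects, lower yield or longer follow-up could let the message arm reach its median.
- *The message will look slower.* This depends on assumed timings. With message-induced tests at 40 or 60 days there is no reversal.
- *The hazard ratio cannot support a claim of faster testing because it rises whenever more patients are tested.* Cumulative percentages and restricted mean time behave the same way. Over all randomised patients, more tests by every time point means earlier testing in that arm. This is no reason to drop the Cox model.

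It can also be said that estimation details belong in a statistical analysis plan, which is not shown. But the choice of the median is stated in the Protocol, and no way of estimating it gives a control-arm value at 9% tested.

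**Conclusion.** The point holds for the summary measure. At the Protocol's 9% usual-care testing rate, the median over all randomised patients will not be reached in the control arm, so no between-arm comparison of such medians is available. In the message arm it is unlikely within one year: about 40% tested if yield stays at 9%, with 50% needing a yield of 7.2% or less at the target diagnosis rate. The remaining option, a median among about 45 and 200 tested patients, departs from intention-to-treat. It can hide the effect (178 against 159 days at a hazard ratio of 5.4) or reverse it, depending on unknown timings (40 to 96 days with the message against 59 in controls).

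This rests on the 9% testing rate applying to the trial's controls, on a horizon of about a year, and, for the message arm only, on constant yield. The primary outcome, the sample size and the Cox comparison are unaffected. It should be corrected, because the aim is a stated one and the correction is cheap.

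**What to change.** In item 12 and in row a of the item 20a table, replace the median with two summaries over all randomised patients, with untested patients censored:

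- the Kaplan-Meier cumulative percentage tested at fixed times, for example days 30, 90, 180 and 365;
- the between-arm difference in restricted mean time to testing up to day 365.

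Report them beside the planned Cox hazard ratio. State the one-year horizon for this outcome. State that a median among tested patients only will not be used to compare the arms.

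The cost is a change of wording in two places. The test dates are already collected under item 18a. The downside is a summary slightly less simple to read than one median in days.
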